9.3. Behavioral Support Compliance

Per protocol, subjects will receive a total of 13 behavioral support sessions at visits: SV2, Day 0, Day 2, Day 3, Day 6, Day 12, Day 16, Day 20, Day 27 EOT, Week 5, Week 6, Week 7 and Week 8.

The total number of behavioural support sessions received will be calculated for each subject and summarized by treatment arm for the Safety Analysis Set. Summaries will also be provided for compliance with behavioral support [(# behavioral support sessions received) / (# behavioral support sessions planned] * 100.

10. EFFICACY ANALYSIS

The efficacy analyses will be conducted using subjects in the All Randomized Analysis Set, as defined in [Section 6.4](#). Subjects will be evaluated by their randomized treatment arm ('intent-to-treat' analysis).

For qualitative endpoints, summary tables will present the number and percentage of subjects for each class of the endpoint. Quantitative endpoints will be summarized by presenting the mean, SD, minimum, median and maximum values. All summary statistics will be presented by treatment arm.

The planned figures for efficacy endpoints are displayed in [Section 15](#).

10.1. Analyses of Primary Efficacy Endpoint

10.1.1. Primary Efficacy Analysis

The two primary objectives, one for each administration schedule (commercial, tid), are stated in [Section 3.1](#). The primary efficacy endpoint, percent of expected cigarettes smoked computed for each subject at end of treatment, is defined in [Section 4.1.1](#).

The distribution of the primary efficacy endpoint for each treatment arm will be displayed by treatment arm using side-by-side box plots. There will be one plot for each administration schedule. Side-by-side box plots will also be provided by treatment arm and BMI class (3 level stratification).

The primary comparisons will compare active arms to the associated placebo arm as follows:

1. 1.5 mg Cytisine – Commercial Schedule vs Placebo – Commercial Schedule
2. 3.0 mg Cytisine – Commercial Schedule vs Placebo – Commercial Schedule
3. 1.5 mg Cytisine – tid Schedule vs Placebo – tid Schedule
4. 3.0 mg Cytisine – tid Schedule vs Placebo – tid Schedule

The primary comparisons will be conducted using an analysis of variance model with fixed effect terms for treatment arm (3 level categorical variable: placebo, 1.5 mg, and 3.0 mg) and BMI class (3 level stratification), and a covariate of baseline cigarettes. There will be one analysis for each administration schedule. The least squares means (LS Means), differences of the LS Means, and their respective 95% CIs will be reported. Forest plots will be used to display 95% CIs for the differences of the LS Means.

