Regarding preliminary pharmacodynamic results, although smokers in the study were not required to have a designated or predetermined quit date, subjects overall in the trial had a significant reduction in number of daily cigarettes smoked by the end of treatment (Figure 1). Mean baseline cigarette consumption in this 18 to 65 year age group was 16.25 (\pm 3.5) cigarettes per day with exhaled CO of 19.9 (\pm 7.3) ppm. By the end of treatment on Day 25, subjects in the 1.5 mg cytisine treatment group were smoking only 8% of the cigarettes compared to baseline cigarette smoking (i.e. a 92% reduction in daily cigarette smoking). Subjects in the 3.0 mg cytisine treatment group were smoking only 5% of the cigarettes compared to baseline cigarette smoking (i.e. a 95% reduction in daily cigarette smoking).

Figure 1: ACH-CYT-02: Percent of Cigarettes Smoked Daily During Study Treatment Compared to Baseline Number of Cigarettes Smoked (N=24)

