7.4. Number of Subjects

A total of 250 subjects will be randomized, with approximately 50 subjects in each of the 4 treatment arms and 25 subjects in each of the two placebo arms. The maximum number of subjects that a single site is allowed to enroll, without consent of the Sponsor, is 50 (approximately 20% of the study total).

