16.2. Efficacy Outcomes

The primary comparisons will be: Arm A versus Arm C, Arm B versus Arm C, Arm D versus Arm F, and Arm E versus Arm F (comparison of active arms to the associated placebo arm).

The primary outcome Y is the percent of expected cigarettes smoked computed for each subject as follows:

Let N=total of number of cigarettes smoked each day over the treatment period from 1 to 25 days.

Let R=representation of the average number of cigarettes smoked daily over the 7-day screening period as baseline.

Let T=number of post-randomization days where number of cigarettes smoked is recorded.

$$\text{Compute } Y = \frac{100 \times N}{T \times R}$$

The denominator is the expected number of cigarettes that would have been smoked without intervention over the days where the number of cigarettes smoked is recorded, and the numerator is 100 times the actual number of cigarettes smoked (the purpose of the 100 factor is to convert to a percent).

The primary analyses will include all randomized subjects by randomized arm (intent-to-treat analysis). The four primary comparisons will be based on analysis of variance with main effects arm (2 levels for the arms to be compared) and BMI class (3 level stratification as previously specified), and with covariate of baseline cigarettes smoked. Sensitivity analyses will include the assessment of the contribution of interaction terms and effect modification analyses. Analyses of data associated with other objectives will be specified in a statistical analysis plan (SAP).

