16.3. Study Size

The trial size is based on projected realization of the effect size estimate for the primary outcome based on data from a Phase 1/2 study in adult smokers. The primary outcome standard deviation from this study was found to be approximately 17. Based on this standard deviation, the estimated between-arm differences in the primary comparisons can be estimated with a 95% confidence interval that is ± 8.3 .

The trial size will not have sensitivity for a dichotomous outcome (e.g. smoking cessation as the secondary efficacy outcome), other than for possibly large differences. For example, if the control

arm outcome is 12% (3/25 defined as successes), then the experimental arm will have a two-sided 95% confidence interval for the probability difference that excludes zero when the success probability is 36% (8/50) or more (computation based on exact confidence interval).

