3.5. Determination of Sample Size

The sample size was computed based on data from a previous Phase 1/2 trial and for achieving narrow confidence intervals (CI) for the primary comparison estimates in this trial.

The trial size was based on projected realization of the effect size estimate for the primary outcome based on data from a Phase 1/2 study in adult smokers. The primary outcome standard deviation from this study was found to be approximately 17. Based on this standard deviation, the estimated between-arm differences in the primary comparisons can be estimated with a 95% CI that is ± 8.3 .

The trial size will not have sensitivity for a dichotomous outcome (e.g. smoking cessation as one of the other efficacy outcomes), other than for possibly large differences. For example, if the control arm outcome is 12% (3/25 defined as successes), then the experimental arm will have a two-sided 95% CI for the probability difference that excludes zero when the success probability is 36% (8/50) or more (computation based on exact CI).

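### The primary ANOVA's single residual variance is an untested assumption with 50/50/25 subjects; arm-specific variances would protect the 95% CIs at almost no cost

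*SAP*

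**What the plan says.** SAP 10.1.1 specifies an "analysis of variance model with fixed effect terms for treatment arm (3 level categorical variable: placebo, 1.5 mg, and 3.0 mg"), together with BMI class and a baseline-cigarettes covariate. It adds: "There will be one analysis for each administration schedule". LS-mean differences with 95% CIs are the reported result. No variance structure, robust standard error or check of spread is written down. Protocol 16.2 describes the same comparisons with "main effects arm (2 levels for the arms to be compared"), so there each model holds only one active arm and its placebo arm.

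Protocol 7.4 plans "approximately 50 subjects in each of the 4 treatment arms and 25 subjects in each of the two placebo arms". Each schedule's SAP model therefore covers 50, 50 and 25 subjects.

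On precision, Protocol 16.3 says: "The primary outcome standard deviation from this study was found to be approximately 17". From this it concludes that the between-arm differences "can be estimated with a 95% confidence interval that is" ±8.3. SAP 3.5 repeats the figure and says the sample size was computed "for achieving narrow confidence intervals (CI) for the primary comparison estimates in this trial". SAP 6.1 sets no alpha level and makes effect-size estimates the overall goal.

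**The concern.** A pooled variance gives correct intervals if the arms have the same spread. When arm sizes are unequal and the smallest arm has a different spread, the pooled estimate is dominated by the larger arms while the standard error of the difference is dominated by the smaller one. The interval is then too narrow if placebo is the more variable arm and too wide if it is the less variable.

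Nothing in the documents tests the assumption. Protocol 16.3 gives one SD, 17, from a Phase 1/2 study that it does not name. The only sponsor study in smokers that the protocol describes is ACH-CYT-02 (Protocol 4.1), an open-label study in which both groups took cytisine. If that is the source, as it appears to be, the 17 carries no information on placebo spread, yet ±8.3 applies it to the placebo arms.

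CI width is the stated basis for the trial's size, so the intervals for the primary comparisons should have close to their nominal coverage.

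**Working it through.** **Inputs.** Arm sizes 50/50/25 (Protocol 7.4). SD 17 (Protocol 16.3), taken here as the active-arm SD. Confidence level 95%. The placebo SD is not given; it is an assumption, shown as a range.

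**The plan's own figure.** SE = 17 × √(1/50 + 1/25) = 17 × √0.06 = 4.164. With t on 73 df (two arms), the half-width is 8.30, which reproduces ±8.3. With t on 122 df (three arms, no covariates) it is 8.24. Both use SD 17 in both arms.

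**Where the information comes from.** Variance degrees of freedom are 49 + 49 = 98 from the active arms and 24 from placebo; 98/122 = 80%. With equal SDs, placebo's share of the variance of a difference is (1/25)/(1/25 + 1/50) = 0.04/0.06 = two thirds.

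**Effect of unequal SDs.** For placebo SD s:
- expected pooled variance = (98 × 17² + 24 × s²)/122
- pooled SE = √(0.06 × pooled variance)
- true SE = √(17²/50 + s²/25)
- approximate coverage = 2Φ(1.980 × pooled SE / true SE) − 1

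Example, s = 25. Pooled variance = (28,322 + 15,000)/122 = 355.1, so pooled SE = 4.616. True SE = √(5.78 + 25) = 5.548. The ratio is 0.832 and approximate coverage is 90.0%.

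| Placebo SD | Pooled SE / true SE | Approximate coverage | Mean half-width, pooled | Mean half-width, separate variances |
|---|---|---|---|---|
| 12 | 1.164 | 97.9% | 7.8 | 6.8 |
| 17 | 1.000 | 95.2% | 8.2 | 8.3 |
| 20 | 0.925 | 93.3% | 8.5 | 9.4 |
| 25 | 0.832 | 90.0% | 9.1 | 11.2 |
| 30 | 0.767 | 87.1% | 9.8 | 13.1 |

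The half-widths are means over 40,000 simulated normal trials without covariates. Simulated pooled coverage agrees with the formula to within about half a point. Separate-variance (Welch) intervals stayed at about 95% throughout.

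**With the SAP's covariates.** A simulation of the full three-arm model (BMI class and baseline covariate, 119 df) gave, by ratio of placebo to active SD: 95.9% at 0.9, 94.9% at 1.0, 93.8% at 1.1, 92.5% at 1.25, 89.5% at 1.5 and 84.8% at 2.0. HC3 standard errors in the same model gave 94.9% to 95.6% at ratios from 0.5 to 2.0.

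**Two-level versus three-level model.** At ratio 1.5 the protocol's two-arm model covers 91.4% and the SAP's three-arm model 89.5%. Pooling the second active arm makes the shortfall somewhat larger when placebo is the more variable arm.

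**Skewed data bounded at zero.** With gamma data (assumed means 25 active, 40 placebo), pooled coverage at placebo SD 20, 25 and 30 was 93.0%, 89.8% and 86.6%. Separate variances gave 94.8%, 94.5% and 93.9%. The result does not depend on normality.

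**The case against.** The strongest objection is that the documents do not show unequal spread. That stands. A reader might infer it from ACH-CYT-02, where "subjects in the 1.5 mg cytisine treatment group were smoking only 8% of the cigarettes compared to baseline cigarette smoking" and the 3.0 mg group 5%, and conclude that the active arms sit against the floor at zero. Those are Day-25 values. The endpoint Y averages over Days 1 to 25, and the quit date is Day 5, 6 or 7. A subject who smokes at the baseline rate until then and stops completely has Y between 4/25 = 16% and 6/25 = 24%. The Day-25 figures therefore do not place Y near its floor.

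A reader might also infer that the CIs in all four primary comparisons will be too narrow. That would need both placebo arms to be more variable than their active arms, and no figure supports it.

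Nor does the point undermine Phase 3 sizing in general. Protocol 7.3.2 ties that mainly to Week 5 to 8 abstinence, which SAP 10.2.1 analyses with exact stratified odds ratios. No decision threshold depends on the coverage of the primary CIs.

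The plan also has partial safeguards. SDs and box plots by arm will make unequal spread visible, but they do not correct the primary CI and no action is tied to them. If the placebo arms look similar, SAP 10.1.2 repeats the analysis with them pooled, roughly 50/50/50. Coverage there is 94.3%, 93.3% and 92.5% at placebo SD 20, 25 and 30, but this is a conditional sensitivity analysis. The 1/SE² weighting in SAP 10.1.2 uses each subject's own daily counts, so it addresses within-subject variation and not between-subject spread by arm.

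Finally, the single variance is inferred from the ordinary meaning of ANOVA; the SAP does not write it out.

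**Conclusion.** The point holds as a conditional, inexpensive improvement. It does not show the plan to be in error. The primary CIs rest on equal spread between placebo and active arms, which the documents neither support nor contradict. If the active SD is 17, coverage of the nominal 95% CI is about 97.8% at placebo SD 12, 93% at 20, 90% at 25 and 87% at 30. An SD difference of about 10% moves it by only about one point; the loss becomes material from about 1.25 to 1.5 times. The direction is unknown.

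This assumes one residual variance in the SAP model, equal SDs in the two active arms, and a placebo SD range that is chosen, not documented.

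**What to change.** In SAP 10.1.1, keep the fixed effects and either estimate the residual variance separately by arm, with Satterthwaite or Kenward-Roger degrees of freedom (in SAS, PROC MIXED with REPEATED / GROUP=arm), or use HC3 standard errors for the LS-mean differences and their 95% CIs. Use the same method in the ANOVA models of SAP 10.1.2.

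In SAP 3.5 and Protocol 16.3, state that ±8.3 assumes a placebo SD of about 17 as well, and give examples: about 9.4 at placebo SD 20 and 11.2 at 25.

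The cost is a sentence in the SAP, a line of code and a note on precision. If the SDs are equal, the mean half-width rises by about 0.1 point (8.33 against 8.23 without covariates). The separate-variance figures above come from unadjusted Welch intervals and the covariate-adjusted ones from HC3; the mixed model itself was not simulated, so a short check before finalising the SAP would be sensible.

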12.1. Procedure Schedule

Table 10 provides a summary of required study evaluations. Refer to Section 12.2 for a detailed description of each study visit. Screening evaluations are to occur within a 28 day interval from initiation of screening evaluations to randomization. Day 1 will be defined as the first day of treatment. Subjects must initiate study treatment the day after randomization, such that study treatment is initiated prior to the quit date, which must be planned within 5-7 days after start of treatment. Both the planned treatment start date and the agreed-upon quit date must be documented at the time of randomization within the source documents and CRF.

Table 10: Schedule of Study Procedures

Study Assessment	Screening Period (Day-28 to Rand)		Randomization	Treatment Period Day 1 through Day 25									Follow-up Assessment Period ¹ (± 3 Days)			
	SV 1	SV 2 ²		Day 0	Day 1 ³	Day 2	Day 3	Day 6 (±1 Day)	Day 12 (±1 Day)	Day 16 (±1 Day)	Day 20 (±1 Day)	Day 27 EOT (±2 Days)	Week 5	Week 6	Week 7	Week 8
Informed Consent	•															
Inclusion/Exclusion	•															
Demographics	•															
Medical and Psychiatric History	•															
SBQ-R questionnaire	•															•
Physical Exam	• ⁴															
Smoking History	• ⁵	• ⁵														
Urine Pregnancy Test for all Females ⁶	•															
Drugs of Abuse Screen ^{6,7}	•															
Vital Signs including Weight	• ⁸		•		•	•	•	•	•	•	•	•	•	•	•	•
Hematology and Chemistry ⁶	•				•	•	•	•	•	•	•	•				•
12-lead ECG	•								•			•				
Concomitant Medications	•	•	•	•	•	•	•	•	•	•	•	•	•	•	•	•
Quit Date Set and Treatment Day 1 Scheduled		•														
Review Diary Completion Instructions	• ⁵		•													
Review Diary for Number of Cigarettes Smoked		• ⁵			•	•	•	•	•	•	•					
Adverse Event Reporting	•	•	•	•	•	•	•	•	•	•	•	•	•	•	•	•
Study Drug Distribution, Accountability and Collection			•		•	•	•	•	•	•	•					

Study Assessment	Screening Period (Day-28 to Rand)		Randomization	Treatment Period Day 1 through Day 25									Follow-up Assessment Period ¹ (± 3 Days)				
	Visit	SV 1		SV 2 ²	Day 0	Day 1 ³	Day 2	Day 3	Day 6 (±1 Day)	Day 12 (±1 Day)	Day 16 (±1 Day)	Day 20 (±1 Day)	Day 27 EOT (±2 Days)	Week 5	Week 6	Week 7	Week 8
Behavioral Support			• ⁹	•		•	•	•	•	•	•	•	•	•	•	•	•
Fagerström Test of Nicotine Dependence				•													
Self-Efficacy Questionnaire				•													
Craving Questionnaire				•		•	•	•	•	•	•	•	•	•	•	•	•
HADS Questionnaire		•							•			•					•

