4.1.1. Primary Efficacy Endpoint

The primary efficacy endpoint will be based on the daily cigarette consumption data recorded in the subject diary. The primary efficacy endpoint is defined as the percent of expected cigarettes smoked computed for each subject, at end of treatment. This percent is designated by Y, Y is calculated as below:

$$Y = \frac{100 \times N}{T \times R}$$

where N represents total number of cigarettes smoked each day over the treatment period from Day 1 to Day 25; T represents number of post-randomization days where number of cigarettes smoked is recorded; and R represents the average number of cigarettes smoked daily over the 7-day screening period as baseline. T*R represents the total number of cigarettes that would have been smoked without intervention over the number of recorded days.

If a subject has no cigarette-count data collected post-randomization, then the primary endpoint will be imputed to a value of 100 (i.e., no change from baseline cigarette consumption). This is equivalent to imputing the total number of post-randomization days with data recorded (T) is 25 and the total number of cigarettes smoked over the treatment period (N) is the average number smoked daily at baseline (R) times 25.

The primary comparisons for this endpoint will be comparisons of active arms to the associated placebo arm, refer to [Figure 1](#):

Arm A (1.5 mg cytosine commercial schedule) versus Arm C (placebo commercial schedule),
Arm B (3.0 mg cytosine commercial schedule) versus Arm C (placebo commercial schedule),
Arm D (1.5 mg cytosine tid schedule) versus Arm F (placebo tid schedule), and
Arm E (3.0 mg cytosine tid schedule) versus Arm F (placebo tid schedule).

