6.7. Interactions and Covariates

Interactions: Assessment of the effect of interaction between treatment (1.5 mg cytisine, 3.0 mg cytisine, placebo) and the BMI stratification factor (18.5 to <25 kg/m²; 25 to <30 kg/m²; 30 to <35 kg/m²) will be included in the sensitivity analyses.

Covariates: Baseline cigarettes smoked, defined as the average number of cigarettes smoked daily over the 7-day screening period.

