8.5. Baseline Smoking and Nicotine Testing

The following baseline data related to smoking will be summarized by treatment arm:

- Average number of cigarettes smoked per day over 7 consecutive days, as reported in the subject diary
- Expired CO (ppm) at SV1
- Expired CO (ppm) at Day 0
- Nicotine metabolism ratio (NMR) at SV1. NMR will be derived as the ratio of the results for 3-hydroxycotinine (3-OH cotinine) and cotinine (i.e., 3-OH cotinine / cotinine).

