8.6. Baseline Questionnaires

Subjects will complete the Suicidal Behaviors Questionnaire – Revised (SBQ-R) and Hospital Anxiety and Depression (HADS) questionnaires at SV1 and the Fagerstrom Test of Nicotine Dependence (FTND), Self-efficacy Questionnaire (SEQ-12), Tobacco Craving Questionnaire (TCQ) and Alcohol Use Questionnaire at Day 0, prior to randomization. The following scores will be derived and summarized at baseline by treatment arm:

- SBQ-R: total score
- HADS: scores for depression and anxiety (see Appendix 5, study protocol)
- FTND: total score
- SEQ-12: internal stimuli score (items 1-6), external stimuli score (items 7-12) and total score (items 1-12)
- TCQ: scores for emotionality, expectancy, compulsivity and purposefulness (see Appendix 4, study protocol), as well as a total score.

In addition, the number and percentage of subjects with each item response on the baseline Alcohol Use Questionnaire will be summarized by treatment arm.

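### The primary model leaves out three baseline variables already collected (FTND total, Day 0 CO, planned quit day), so the primary intervals may be wider than necessary

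*SAP*

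**What the plan says.** The SAP's primary model (10.1.1) has a three-level arm term "and BMI class (3 level stratification), and a covariate of baseline cigarettes", fitted once per schedule. The protocol's version (16.2) has "main effects arm (2 levels for the arms to be compared) and BMI class (3 level stratification as previously specified"), again with baseline cigarettes. SAP 6.7 names a single covariate: "Baseline cigarettes smoked, defined as the average number of cigarettes smoked daily over the 7-day screening period". The same quantity is the divisor of the endpoint, since in SAP 4.1.1 "R represents the average number of cigarettes smoked daily over the 7-day screening period as baseline" and Y = 100·N/(T·R).

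Three other baseline variables are collected:

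- **FTND.** SAP 8.6 lists "the Fagerstrom Test of Nicotine Dependence (FTND), Self-efficacy Questionnaire (SEQ-12") and other questionnaires as completed on Day 0 before randomization.
- **Expired CO.** SAP 8.5 lists "Expired CO (ppm) at Day 0" among the baseline data. Protocol 12.2.2 places it ahead of the randomization step.
- **Planned quit day.** This is Treatment Day 5, 6 or 7. Protocol 12.1 requires that "the agreed-upon quit date must be documented at the time of randomization within the source documents and CRF".

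SAP 10.1.2 uses baseline CO and the questionnaire scores only to look for effect modification, one factor at a time with an arm-by-factor interaction. Planned quit day is not named there, although the list is open-ended. The repeat models in that section remove baseline cigarettes or BMI class; none adds a prognostic term.

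**The concern.** Precision is the only sizing criterion. SAP 3.5 justifies the sample size by interval width, and SAP 6.1 sets no significance level. Each contrast compares about 50 subjects with about 25 on placebo, and randomization is stratified by BMI class alone. In that setting, baseline variables that predict Y are worth using, because variation they could explain otherwise stays in the error term.

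The one continuous covariate is R. It may still help, but Y has already been scaled by it, so part of its information has been spent. Planned quit day has a link to Y that follows from the endpoint's arithmetic: Y averages over 25 days, so each day of delay before stopping can move it by up to 100/25 = 4 points. What is at stake is a few percent of interval width on the four primary contrasts, in either direction.

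**Working it through.** **Inputs from the documents.** For the SD, Protocol 16.3 states: "The primary outcome standard deviation from this study was found to be approximately 17". Arm sizes are 50 and 25 (Protocol 7.4), confidence is 95%, and the stated half-width is ±8.3.

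**Input not in the documents.** The additional R² of the three covariates, given BMI class and baseline cigarettes, is assumed over 0 to 0.20.

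**1. The plan's own figure.** SE = 17 × √(1/50 + 1/25) = 4.164. With t on 73 df (1.993), the half-width is 8.299, which matches ±8.3. This is an unadjusted two-sample figure and credits nothing to covariates.

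**2. Reference for the SAP model.** Three arms give 125 subjects. The model has six parameters (intercept, two arm, two BMI class, one baseline cigarettes), so df = 119. With no variance reduction credited, 1.9801 × 4.164 = 8.25.

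**3. Adding three linear covariates.** df = 116, and

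half-width = t(0.975, 116) × 4.164 × √(1 − R²) × √(1 + 3/115).

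The last factor (1.013) is the expected cost of chance imbalance in three extra covariates. Before R² is applied, the product is 1.9806 × 4.164 × 1.013 = 8.35.

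| Assumed additional R² | Half-width | Change from 8.25 |
|---|---|---|
| 0 | 8.35 | 1.3% wider |
| 0.05 | 8.14 | 1.2% narrower |
| 0.10 | 7.93 | 3.9% narrower |
| 0.20 | 7.47 | 9.4% narrower |

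In equivalent sample size, 0.10 is worth about 8% more subjects and 0.20 about 22% more. A least-squares simulation with 4,000 runs per R² value gave width ratios within 0.002 of these.

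**4. Break-even.** 1 − (8.245/8.354)² = 0.026. Below that, the added covariates widen the interval.

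**5. Planned quit day alone.** Suppose a subject smokes at the baseline rate until the planned day and then stops completely. Y is then 100 × (d − 1)/25, which is 16, 20 or 24 for d = 5, 6 or 7. With quit days evenly spread (assumed), the SD is 4 × √(2/3) = 3.27. The share of variance is (3.27/17)² = 0.037, and √(1 − 0.037) = 0.981, so the interval is about 2% narrower before the covariate's own cost. If smoking only halves on the day, the share falls to 0.009 and the gross gain to about 0.5%.

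**6. Dependence on the model form.** If the protocol's two-arm model were fitted separately for each contrast, df would be 70 without the covariates (8.31) and 67 with them. At R² = 0 the latter gives 1.9960 × 4.164 × √(1 + 3/66) = 8.50, which is 2.3% wider. The 1.3% cost therefore applies to the SAP's three-arm model.

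**The case against.** The strongest reply is that nothing in the documents shows these variables predict Y once BMI class and baseline cigarettes are in the model. That stands. A reader might infer that the intervals are definitely too wide, but the documents do not support this: no correlation is given, and below an additional R² of 0.026 the change makes them wider.

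A reader might also scale the stated ±8.3 by √(1 − r²) and claim the result as the gain. That overstates it. The ±8.3 is not the SAP model's width, and the scaling ignores the cost of the added terms. At a joint r of 0.3 (R² = 0.09), it suggests about 10% more subjects; the net figure against 8.25 is about 7%.

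Three further points stand:

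- FTND includes a cigarettes-per-day item (Protocol Appendix 2), so it overlaps with R.
- The quit-day calculation is a ceiling. Protocol 12.2.6 anticipates lapses after the quit date, and SAP 4.1.2 allows roughly two and a half weeks of grace.
- Randomization makes the planned contrasts valid, and their intervals already allow for chance imbalance. No actual imbalance is known.

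The reply that SAP 10.1.2 already covers the matter holds only in part. Its models describe treatment effects within levels of one factor. They do not report an overall contrast adjusted for these variables.

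**Conclusion.** The point holds as a conditional efficiency suggestion, not as an error in the plan. The primary analysis is valid, and its stated precision is met if the SD is 17. Three pre-randomization variables are collected but not used as prognostic covariates for the primary contrasts.

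Adding them changes the half-width by between +1.3% and −9.4% over an assumed additional R² of 0 to 0.20. Planned quit day contributes about 2% at most under even spread and full cessation on the day. These figures rest on SD 17, arms of 50 and 25, the SAP's three-arm model and linear covariate effects. The case for acting is that the downside is small and bounded, the data are already collected, and interval width is what the trial was sized for.

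**What to change.** Before unblinding, pre-specify FTND total, Day 0 expired CO and planned (not actual) quit day as main-effect covariates beside BMI class and baseline cigarettes. The planned day matters because the actual quit day is observed after randomization and could be affected by treatment. There are two routes:

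- put the covariates in the primary model in SAP 10.1.1 and amend the model in Protocol 16.2 to match; or
- keep the protocol model as primary and add one named supportive model to SAP 10.1.2, reporting both intervals.

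State a simple rule for missing covariate values, for example single imputation with the overall baseline mean, blind to arm. Without one, a standard fit would drop any subject lacking an FTND or CO value, although the analysis is meant to include everyone randomized and SAP 4.1.1 already imputes Y for subjects with no cigarette counts.

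The cost is SAP wording, plus a protocol amendment on the first route. Statistically it is about 3 degrees of freedom, roughly 1% in width under the SAP model if the covariates prove uninformative. No new data collection is needed.
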